4.2.6. COPIES OF VM202 IN WHOLE BLOOD

The number of copies of VM202 in whole blood will be determined by PCR at Day 0 (pre-injection, and 1 to 3 hours post injection), Day 14 (pre-injection, and 1-3 hours post injection), Day 21, 30, 60, and Day 90. Whole blood will be collected in EDTA-coated tubes, inverted >5 times and transferred to plastic sterile and or RNase and DNase free vials of ~0.6 cc aliquots each. Collect 5 cc of whole blood per patient per timepoint (meaning a transfer to a minimum of 5 vials containing 0.6cc – 1cc aliquots). The vials will be snap frozen in LN2 or an alcohol dry ice bath. These will be maintained in a \leq -65°C freezer until shipped for analysis. Samples should be labeled with subject ID, draw date and time, study number, and visit

interval (i.e., Day 0, 14, 21, 30, 60 or 90). All sample packages will be sent in a single batch, including serum HGF samples) with a temperature tracking recorder. Analysis will be conducted by Charles River Laboratories in accordance with good laboratory practices (GLP). Samples should be sent to:

Charles River Laboratories Preclinical Services Nevada [name] [contact]

4.2.7. PHOTOGRAPH AND MEASUREMENT OF ULCER

Two photographs of any ulcerations or gangrenous areas will be taken for documentation purposes only if present at screening or immediately before treatment on Day 0. If present prior to the first injection, two photographs of each ulceration/gangrene area will be obtained at Day 30, Day 60, Day 90, 6 months and 12 months. A metric ruler (cm and mm) will be photographed in the lower right hand corner of the frame to allow for scale determination. During the monitoring visit, the monitor will retrieve one of the two photographs for each ulceration/gangrene area. The border of all photographs will be labeled with the photograph date, patient's initials, and the patient's study number assignment. Ulcer dimensions will be recorded.

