1.4. VM202

The investigational agent being studied in this protocol is VM202. VM202 is a DNA plasmid that contains novel genomic cDNA hybrid human hepatocyte growth factor (HGF) coding sequence (HGF-X7) expressing two isoforms of HGF, HGF 728 and HGF 723.

The key feature of HGF-X7 is that it was designed by inserting a series of intron sequences into certain sites of HGF cDNA so that both isoforms of HGF protein are expressed simultaneously and efficiently as in the human genome. Because there is no change in the coding region of the HGF gene, HGF proteins generated from

VM202 are identical to the wild-type human HGF proteins. VM202 has been developed using the pCK DNA plasmid that has been safely used in previous ViroMed-sponsored clinical trials with VEGF as the therapeutic gene, known as VMDA-3601.

[figure not shown]

Figure 2. VM202 construct

Safety of VM202. The use of plasmids for targeted delivery of angiogenic factors into muscle tissue is a particularly attractive and a relatively safe therapeutic approach, because plasmids have been shown to effectively transfect postmitotic cells such as skeletal and heart muscle and to successfully express angiogenic genes with very little dissemination and persistence at distant sites. Following intramuscular injection, the plasmid that persists is extrachromosomal and integration into host DNA, if it occurs, is negligible. 43-45 This local effect of conventionally injected naked plasmid DNA is well known. 46, 47

Potential Efficacy of VM202. VM202 has demonstrated potential for stimulating angiogenesis in animal models. The development of new blood vessels may improve blood flow to peripheral nerves and potentially replace damaged capillary bed. As there is some overlap in the pathology of critical limb ischemia and diabetic neuropathy, ⁴⁸ VM202 may have the ability to decrease neuropathic pain, and improve patient quality of life and exercise capacity.

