Preliminary Conclusions. These early data support the feasibility of intramuscular injections of VM202 in patients with critical limb ischemia. Results suggest that this therapeutic approach may improve functional outcomes and provide symptomatic relief. VM202 is rapidly eliminated from circulation, and appears to remain active only at the injection site. The incidence of complications, while high, did not appear to be significantly different between treatment cohorts. Continued study of VM202 in patients with CLI and / or diabetes is warranted.

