If a DLT is observed in a patient in a dose cohort with complete enrollment, but after a dose escalation has occurred, further dose escalation may be delayed pending review of the data. If 2 patients in a dose cohort experience a DLT, then the study will be stopped.

A DLT is defined as any of the following SAEs:

- acute anaphylaxis (including erythema, hives, wheezing, stridor or respiratory distress) attributable to VM202 injection;
- temperature >102°F with negative blood cultures and in absence of viral syndrome within 24 hours of study drug administration; or
- evidence of active tissue necrosis of grade 3 or greater at the injection site within two weeks of study drug administration.

The DSMB will make a formal recommendation to proceed (or not proceed) to the next dose cohort between the first and second dose cohort, and again between the

second and third dose cohort (if applicable). The DSMB will monitor patient safety throughout the 12 month follow-up period.

[figure not shown]

Figure 3. Study flowchart

Screening/Baseline assessments should occur within the 60 days prior to Day 0 (day of injection). Baseline assessments include assessment of study eligibility, a complete medical history, vital signs, complete physical exam, photograph and measurement of ulcers (if any), cancer screening tests, viral screening, MNSI Score, VAS, 12 lead EKG, retinal fundoscopy, clinical chemistry, hematology, urinalysis, and pregnancy test (women of childbearing potential only), and documentation of any ulcers or gangrenous areas.

Patients will be treated with 8, 16 or 32 – 0.5 mL intramuscular injections in the right calf of VM202 on Day 0 and again on Day 14. Each injection will contain 0.25 mg VM202. The first cohort of patients will receive a total dose of 4 mg of study product in 8 mL of solution (eight injections on Day 0, and eight injections on Day 14). The second cohort of patients will receive a total dose of 8 mg of study product in 16 mL of solution (sixteen injections on Day 0, and sixteen injections on Day 14). The third cohort of patients will receive a total dose of 16 mg of study product in 32 mL of solution (thirty-two injections on Day 0, and thirty-two injections on Day 14).

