3.3.2. EXCLUSION CRITERIA

- 1. Peripheral neuropathy caused by condition other than diabetes;
- 2. Other pain more severe than neuropathic pain;
- 3. Progressive or degenerative neurological disorder;
- 4. Myopathy;
- 5. Have an inflammatory disorder of the blood vessels (inflammatory angiopathy, such as Buerger's disease);
- 6. Active infection;
- 7. Chronic inflammatory disease (e.g. Crohn's, Rheumatoid Arthritis)
- 8. Positive HIV or HTLV
- 9. Positive Hepatitis B or C as determined by Hepatitis B core antibody (HBcAB), antibody to Hepatitis B antigen (IgG and IgM; HbsAB), Hepatitis B surface antigen (HBsAg) and Hepatitis C antibodies (Anti-HCV), at Screening or known immunosuppression or on chronic treatment with immunosuppressive drugs, chemotherapy or radiation therapy;
- 10. Stroke or myocardial infarction within last 6 months;
- 11. Ophthalmologic conditions pertinent to proliferative retinopathy or conditions that preclude standard ophthalmologic examination:
 - Cataract surgery within 6 months of trial;
 - Vascular lesions of the anterior segment of the eye (infection or ulceration of the cornea, rubeotic glaucoma, etc);
 - Vascular lesions of the posterior segment of the eye or proliferative retinopathy, macular edema, s/p photocoagulation for macular edema or proliferative retinopathy; sickle cell retinopathy, ischemic retinopathy due to retinal venous stasis or carotid artery disease;
 - Choroidal angiogenesis; and
 - Large elevated choroidal nevi, choroidal vascular tumors (choroidal hemangioma), or melanomas.
- 12. Specific laboratory values at Screening including: Hemoglobin < 9.0, g/dL, WBC < 3,000 cells per microliter, platelet count <75,000/mm3, Creatinine > 2.0 mg/dL; GFR < 50, AST and/or ALT > 2 times the upper limit of normal or any other clinically significant lab abnormality which in the opinion of the investigator should be exclusionary;
- 13. Use of gamma-linolenic acid (GLA), alpha lipoic acid or any other high dose dietary antioxidant supplement for symptomatic relief of DPN;
- 14. Uncontrolled hypertension as defined as sustained systolic blood pressure (SBP) > 200 mmHg or diastolic BP (DBP) > 110 mmHg at baseline/screening evaluation;
- 15. Patients with a recent history (<5 years) of or new screening finding of malignant neoplasm except basal cell carcinoma or squamous cell carcinoma of the skin (if excised and no evidence of recurrence);

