Appendix 8. Visual Analog Scale

Completion of the VAS is based on pain that the subject is experiencing in the right leg (pain below the knee which may include the calf, foot, or both). If the right leg is medically contraindicated, the left leg will be assessed. A score of > 4 cm (40 mm) is required in order to be eligible for the study.

The VAS will be completed by the subject. The subject should be asked: "How do you currently rate your pain in your leg (below the knee - this includes pain in your foot) that will undergo/underwent study injections? Please place one tick mark on the line below."

The subject should be instructed to indicate his or her current level of pain in the affected leg associated with diabetic neuropathy by placing a single vertical line perpendicular to the horizontal line of the scale ensuring that the two lines intersect. Additionally, the subject should be instructed to not use a check mark, "x" or circle that would intersect the horizontal line of the scale multiple times. Ensure the subject understands that the mark must be only one line that is perpendicular to and intersects the scale line. The subject should complete the VAS with a fine or medium point pen; felt tip pens and pencils should not be used.

The VAS should be checked for accuracy and completeness immediately after it is completed by the subject. If the subject's mark does not intersect the line or intersects the line more than once, reinstruct the subject to modify his or her mark so it meets the appropriate criteria. Any corrections should be accompanied by the subject's initial and date. For Days 0 and 14, all corrections MUST be completed prior to injections; do NOT have the subject correct the scale after injections. Instead, use the data collected prior to dosing.

The VAS score (0 to 100mm) will be calculated by measuring the distance from the left end of the line ("No Pain") along the scale to the mark made by the subject. If the mark made by the subject intersects the horizontal line of the scale multiple times and was not corrected, measure to the middle point between the two marks. If the mark made by the subject does not intersect the line of the scale and was not corrected, project the location of the mark vertically to a point on the line of the scale for the measurement

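### Coexisting ischaemic leg pain or gangrene is neither excluded nor flagged, so relief of ischaemic pain from an angiogenic agent could be counted as relief of neuropathic pain

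*Combined protocol and SAP*

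**What the plan says.** **Gangrene at entry.** The screening assessments in Section 3.2 include "documentation of any ulcers or gangrenous areas". Section 4.2.7 adds "Two photographs of any ulcerations or gangrenous areas will be taken for documentation purposes only if present at screening"; lesions first seen just ahead of the Day 0 injections count as well. The same section then says "If present prior to the first injection, two photographs of each ulceration/gangrene area will be obtained at Day 30", continuing at later visits to 12 months.

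**Eligibility.** The exclusion list appears twice, in the Synopsis and in Section 3.3.2, with 24 items each time. Two bear on this point. Exclusion 2 is "Other pain more severe than neuropathic pain". Exclusion 5 covers an "inflammatory disorder of the blood vessels (inflammatory angiopathy, such as Buerger's disease". Neither list names peripheral arterial disease, limb ischaemia, ischaemic rest pain or gangrene. Ankle-brachial index stands in the Glossary but in no screening list or visit schedule.

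**The agent.** Section 1.4 calls VM202 potentially angiogenic and links the two diseases: "As there is some overlap in the pathology of critical limb ischemia and diabetic neuropathy". The preliminary conclusions from earlier patients with critical limb ischaemia say: "Results suggest that this therapeutic approach may improve functional outcomes and provide symptomatic relief".

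**Pain measurement.** The VAS question in Appendix 8 is "How do you currently rate your pain in your leg (below the knee - this includes pain in your foot", asked of the leg that is injected. The instruction that follows tells the subject to mark pain associated with diabetic neuropathy. The BPI-DPN asks about pain the patient attributes to diabetes. The SF-MPQ form as reproduced in Appendix 5 names no cause.

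**Analysis.** Section 6.2 makes pain a secondary endpoint. Section 6.2.3 tabulates it descriptively and also reports preexisting ulcers. Section 6 rules out hypothesis tests.

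**The concern.** Most competing pains in a neuropathy trial add noise with no particular direction. Ischaemic pain differs here because the protocol itself suggests that VM202 may relieve symptoms in limb ischaemia. If a patient has both conditions, the ischaemic part may fall after treatment and lower the recorded score. Any resulting error in the pain summary is toward benefit. With no control arm nothing offsets it, and with four patients per cohort one person carries a quarter of the mean. As written, the plan gives the reader of the pain tables no way to see whether this has happened.

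**Working it through.** **Step 1: sample size.** 3 cohorts × 4 patients = 12. Adding 2 for one expansion after a dose-limiting toxicity gives 14. Both match the Synopsis. The plan has no power or effect-size figure to reproduce.

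**Step 2: who can enter.** Read together, the criteria leave this gap:
- ischaemic pain worse than the neuropathic pain: barred by exclusion 2;
- ischaemic pain equal to or less than the neuropathic pain: not barred;
- gangrene: barred only if another criterion applies, such as active infection (exclusion 6);
- limb-vessel disease: barred only if inflammatory (exclusion 5).

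**Step 3: can the instruments separate the two pains?**
- VAS: the question covers all pain below the knee in the treated leg, while the instruction narrows it to neuropathic pain. The result depends on the patient telling apart two pains in one foot.
- BPI-DPN: attribution to diabetes does not distinguish ischaemia from neuropathy in a diabetic patient.
- SF-MPQ: no cause is named on the form.

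The screening VAS also serves as the pain threshold for entry, so ischaemic pain could help a patient qualify.

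**Step 4: size if it happens (illustration, all inputs assumed).** Let *f* be the VAS fall due to ischaemic relief, *k* the number of such patients and *n* the number averaged. The shift in the mean is *k* × *f* / *n*.

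| *f* (cm) | *k* | *n* | Shift in mean (cm) |
|---|---|---|---|
| 2 | 1 | 4 | 2/4 = 0.5 |
| 4 | 1 | 4 | 4/4 = 1.0 |
| 6 | 1 | 4 | 6/4 = 1.5 |
| 4 | 1 in the whole trial | 12 | 4/12 = 0.33 |
| 4 | 3 (one per cohort) | 12 | 12/12 = 1.0 |

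**Step 5: chance that at least one such patient enrols.** The documents give no prevalence. For an assumed prevalence *p* among enrolled patients, the chance is 1 − (1 − *p*)^*n*.

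| *p* | *n* = 4 | *n* = 12 |
|---|---|---|
| 5% | 19% | 46% |
| 10% | 34% | 72% |
| 20% | 59% | 93% |
| 30% | 76% | 99% |

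This is the chance that a patient with limb ischaemia is enrolled, not the chance that the pain result is distorted. Distortion also requires ischaemic pain, relief of it, and a rating that captures that relief.

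**The case against.** The case against is substantial, and several parts of it stand.

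- *Ischaemic pain is not unrestricted.* Exclusion 2 bars it when it is the worse pain, and patients need diagnosed painful neuropathy in both legs and an MNSI examination score of at least 3. This stands and narrows the gap. It does not close it: foot appearance and ulceration each score 1 per foot, so inspection alone can give 2 × 2 = 4 points without any reflex or sensory deficit.
- *The instruments try to direct the rating.* This also stands. A reader might infer that ischaemic relief will be reported as neuropathic relief. The documents support only that it could be.
- *A vascular effect is not off-target.* Section 1.4 proposes better blood flow to peripheral nerves as a way of reducing neuropathic pain. A reader might infer that any vascular benefit is spurious, and the protocol's own rationale contradicts that. The narrower question is whether a patient improved because a separate ischaemic pain was relieved.
- *The evidence of response is thin.* The sentence on critical limb ischaemia speaks of symptoms in general and is tentative. The detailed results are not in the text available for review, so the size of any effect on pain cannot be checked.
- *The photography text is conditional.* It shows that gangrene is admissible, not that it is expected. Likewise, the alternative causes in Section 4.1.1 are examples of causes of neuropathy, so silence there on ischaemia proves little.
- *Consequences are limited.* Pain is secondary, descriptive and untested, and the open-label, uncontrolled design already prevents causal claims. This stands.

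A reader might also infer that such patients would distort the safety comparison, because complications in the limb ischaemia patients are described as frequent. The documents do not support this. Dose-limiting toxicity is confined to three narrow events, no safety test is planned, and that complication rate belongs to a different population.

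**Conclusion.** The point holds in limited form. Gangrene and coexisting ischaemic pain no worse than the neuropathic pain can enter the study, and the plan does not identify such patients in the pain tables. Relief of that pain could be counted as relief of neuropathic pain, with a bias toward apparent benefit.

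One such patient would move a four-patient cohort mean by 0.5 to 1.5 cm, on an assumed fall of 2 to 6 cm. The upper end is hard to reach, because exclusion 2 leaves only ischaemic pain that is the lesser or equal component. Over 12 patients, an assumed 4 cm fall gives 0.33 cm with one such patient in the trial and 1.0 cm with one in each cohort. The number of such patients, their VAS fall and its cause are all assumptions.

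The primary safety objective is unaffected. The case for acting is that pain is the study's main efficacy signal and the remedy is cheap.

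**What to change.** At Day 0, before injection, flag each patient with gangrene or ischaemic rest pain, using the history, physical examination and ulcer/gangrene documentation already required. In Section 6.2.3, state that VAS, SF-MPQ and BPI-DPN will be tabulated with and without flagged patients. With four per cohort, also show the flag in a by-patient listing.

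Alternatively, the sponsor may exclude these patients at screening. That is more debatable, since the plan also means to report preexisting ulcers.

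The flag costs one data field and a set of repeat tables; it needs no new test and loses no patients. Exclusion would cost a few more screen failures. Either way, without a perfusion test some limb ischaemia will be missed, and the report should say so.

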4.2.8. VISUAL ANALOG SCALE (VAS) SCORE

Pain will be measured using the visual analog scale (VAS) at screening, before the first treatment (injection) on Day 0, before the second treatment (injection) on Day 14, at Day 30, Day 60, Day 90, 6 months and 12 months. The VAS scoring instrument is a 10-cm line, oriented horizontally, with the left end indicating "no pain" and the right end representing "pain as bad as it can be". The patient is asked to mark a place on the line corresponding to the current pain intensity. The distance along the scale is then converted into a numeric reading by measuring the distance of the patients mark in centimeters from the beginning of the scale (the 0 mark). The VAS is illustrated in Appendix 8.

4.2.9. SHORT FORM McGILL PAIN QUESTIONNAIRE (SF-MPQ)

Pain will also be characterized using the Short Form version of the McGill Questionnaire (SF-MPQ).⁵² This questionnaire reviews 15 dimensions of pain: descriptors 1-11 represent the sensory dimension of pain experience and 12-15 represent the affective dimension. Each descriptor is ranked on an intensity scale of 0 = none, 1 = mild, 2 = moderate, 3 = severe. This test will be administered preinjection on Day 30, Day 60, Day 90, 6 months and 12 months. The SF-MPQ can be found in Appendix 5.

4.2.10. Brief Pain Inventory for Patients with Diabetic Peripheral Neuropathy (BPI-DPN)

The brief pain inventory (BPI-DPN)⁵³ will be administered before the first treatment (injection) on Day 0, on Day 30, Day 60, Day 90, 6 months and 12 months. The full Questionnaire can be found in Appendix 6.

4.2.11. INJECTION SITE REACTION ASSESSMENT

Local injection sites reactions will be assessed on Day 0 post injection, Day 14, Day 21, Day 30 and Day 60 using the grading defined by the National Cancer Institute's Common Terminology for Adverse Events v3.0. The grading categories are as follows and will be recorded on the CRF as described in

Table 3. Injection Reaction Assessment

Table 3.

ADVERSE EVENT	GRADE 1	GRADE 2	GRADE 3	GRADE 4	GRADE 5
Injection site reaction	Pain, itching, erythema	Pain or swelling, with inflammation or phlebitis	Ulceration or necrosis that is severe; operative intervention indicated		
Ulceration		Superficial ulceration < 2 cm size; local wound care; medical intervention indicated	Ulceration ≥2 cm size; operative debridement, primary closure or other invasive intervention indicated (e.g. hyperbaric oxygen)	Life- threatening consequences; major invasive intervention indicated (e.g., complete resection, tissue reconstruction, flap, or grafting	Death
Allergic reaction / hypersensitivity	Transient flushing or rash; drug fever < 38°C (<100.4°F)	Rash; flushing ; urticaria; dyspnea; drug fever ≥38°C (≥100.4°F)	Symptomatic bronchospasm, with or without urticaria; parenteral medications(s) indicated; allergy- related edema/ angioedema; hypotension	Anaphylaxis	Death

5. **EVALUATION OF ADVERSE EVENTS**

5.1. **DEFINITIONS**

An Adverse Event (AE) is the development of an untoward medical occurrence or the deterioration of a pre-existing medical condition following or during exposure to an investigational product, whether or not considered causally related to the product.

An untoward medical condition can be symptoms (e.g., nausea, chest pain), signs (e.g., tachycardia, enlarged liver) or clinically significant abnormal results of an investigation (e.g., laboratory findings, electrocardiogram).

A serious adverse event (SAE) is any untoward medical occurrence which:

- Results in death;
- Is life-threatening;
- Requires inpatient hospitalization or prolongation of hospitalization which is not specifically required by the protocol or is elective;
- Results in permanent impairment of a body function or permanent damage to a body structure; or
- Requires medical or surgical intervention to preclude permanent impairment of a body function or permanent damage to a body structure.

Additionally, important medical events that may not result in death, be lifethreatening or require hospitalization may be considered SAEs when they jeopardize the patient or require medical or surgical intervention to prevent one of the serious outcomes listed above. Examples of such medical events include: allergic bronchospasm requiring intensive treatment in an emergency room or at home, blood dyscrasias or convulsions that do not result in inpatient hospitalization or the development of drug dependency or drug abuse. Medical and scientific judgment must be exercised when classifying events as serious.

Life-threatening means that the patient is, in the view of the investigator, at immediate risk of death from the AE as it occurred. It does not include an AE which, had it occurred in a more serious form, might have caused death.

Persistent or significant disability/incapacity means that the event resulted in permanent or significant and substantial disruption of the patients' ability to carry out normal life functions.

An unexpected AE is an AE, the nature or severity of which is not consistent with the applicable product information (e.g. Investigator Brochure for an unapproved product). Expected means that the event has been previously observed with the test article and is identified and/or described in the applicable product information. It does not mean that the event is expected with the underlying disease(s) or concomitant medications. It is expected that certain disease states will have reoccurring adverse events some of which may be considered expected over time.

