3.4.5.1. PRE-INJECTION (WITHIN 4 HRS PRIOR TO INJECTIONS)

- Concomitant Medications
- Vital Signs
- Serum Chemistry and hematology
- Serum HGF
- Copies of VM202 in whole blood
- Photograph and measurement of ulcer(s) if present
- Visual Analog Scale (VAS) score
- Short Form McGill Pain Questionnaire (SF-MPQ)
- Brief Pain Inventory for Diabetic Neuropathy (BPI-DPN)

1ST Dose of VM202 3.4.5.2.

• Intramuscular injections of VM202 in calf (unilateral, right leg only unless contraindicated)

3.4.5.3. **POST-INJECTION**

- Vital Signs
- Copies of VM202 in whole blood (2 hours \pm 1 hour post injection)
- Injection site assessment
- Adverse event assessment

DAY 14 ± 1 DAYS -2^{ND} INJECTIONS 3.4.6.

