Appendix 1. Schedule of Evaluations and Visits

SCHEDULE OF EVALUATIONS AND VISITS

	Screening / Baseline (-60 – 0 D)	1 st Injection Day 0		2 nd Injection Day 14 ± 1 D		Day 21	Day 30	Day 60	Day 90	6	12 months	Early
Procedure		Pre- dose	Post- dose	Pre- dose	Post- dose	± 3 D	± 3 D	± 7 D	± 7 D	months ± 1 mo	± 1 mo	Withdrawal
Baseline Evaluation												
Informed Consent	✓											
Complete Medical History	✓											
Complete Physical Exam	✓											
Cancer screening [†]	✓											
Viral screening – HIV, HTLV, HBV, HCV	✓											
Urinalysis	✓											
MNSI ††	✓											
EKG	✓											
Pregnancy test	✓											
Safety and Efficacy Parameters												
Retinal Fundoscopy	✓										✓	✓
Concomitant Medications	✓	✓		✓		✓	✓	✓	✓	✓	✓	✓
Serum Chemistry and hematology	✓	✓		✓		✓	✓	✓	✓	✓	✓	✓
HbA1c	✓						✓		✓	✓	✓	✓
Photograph and measurement of ulcer(s) ^{†††}	✓	✓					✓	✓	✓	✓	✓	✓
Visual Analog Scale (VAS) score	✓	✓		✓			✓	✓	✓	✓	✓	
Vital Signs	✓	✓	✓	✓	✓	✓	✓	✓	✓	✓	✓	✓
Serum HGF		✓		✓			✓	✓				✓²
Copies of VM202 in whole blood		✓	√ ***	✓	√ ***	✓	✓	✓	✓			✓¹
SF-MPQ *		✓					✓	✓	✓	✓	✓	
BPI-DPN**		✓					✓	✓	✓	✓	✓	
Treatment												
Injection site reaction assessment			✓	✓	✓	✓	✓	✓				✓²
Adverse Events			✓	✓	✓	✓	✓	✓	✓	✓	✓	✓

[†] Includes: cancer markers; chest X-ray or CT scan of the chest (if patient has a previous history of tobacco use, a CT scan will be performed instead of the chest X-ray) within 3 months; pap smear and mammogram if not performed within past 12 months (females only); PSA (males only); for patients ≥ 50 years old, colonoscopy within past 10 years

††† If present prior to first study drug administration

** BPI-DPN - Brief Pain Inventory, diabetic neuropathy specific test

*** 2 hours after injection (± 1 hour)

- 1 If withdrawal occurred before Day 90 Visit
- 2 If withdrawal occurred before Day 60 Visit

[figure not shown]
^{††} MNSI - Michigan Neuropathy screening Instrument

^{*} SF-MPQ - Short Form McGill Pain Questionnaire

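### Injection-site reactions are not assessed before the first Day 0 injection and Table 3 grades are tied to no baseline, so existing leg symptoms and mild (Grade 1) reactions can be confused in either direction.

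*Combined protocol and SAP*

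**What the plan says.** **Timing.** Section 4.2.11 sets the schedule: "Local injection sites reactions will be assessed on Day 0 post injection, Day 14, Day 21, Day 30 and Day 60". The visit lists agree. The Day 0 pre-injection list (3.4.5.1) omits the assessment and the Day 0 post-injection list (3.4.5.3) has it. In Appendix 1, the row "Injection site reaction assessment" has its first tick under Day 0 post-dose. At Day 14 the assessment is ticked both before and after dosing.

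**Grading.** In Table 3, Grade 1 is "Pain, itching, erythema" and Grade 2 is "Pain or swelling, with inflammation or phlebitis". Neither the table nor the text around it says what the finding is to be compared with.

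**Entry pain.** Appendix 8 says: "A score of > 4 cm (40 mm) is required in order to be eligible for the study". The score refers to the leg that will be injected, and the region is "pain below the knee which may include the calf, foot, or both". Appendix 4 spreads the injections over the calf of that leg.

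**Baseline information.** VAS, SF-MPQ and BPI-DPN are all taken before injection on Day 0 (3.4.5.1), and the BPI-DPN includes a body diagram on which the patient shades the painful areas. A physical examination covering extremities and skin is done at screening only (4.1.2, Appendix 1), which may be up to 60 days before Day 0.

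**Adverse event rules.** Section 5.1 defines an adverse event as something that develops, or an existing condition that deteriorates. Section 4.1.1 assigns new findings before the first dose to medical history. Section 5.2 records the relationship to underlying disease as well as to drug and procedure.

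**The concern.** Safety and tolerability is the primary endpoint (6.2), and local reactions are an obvious tolerability signal when each treatment day brings 8, 16 or 32 injections into one calf. The study is open label with no control arm, and Table 3 is not applied to the uninjected leg. The only comparator for a local finding is the same calf before the first injection.

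A patient whose neuropathic pain already reaches the calf could satisfy the pain wording of Grade 1 with no injection effect. The error can also run the other way: an assessor who knows the patient has painful neuropathy may put down real, mild injection pain to the disease. With 4 patients per cohort, one such decision visibly changes a cohort's reaction rate, and the cohorts are the dose comparison. The DSMB's escalation review covers adverse events as well as DLTs (3.2), so these grades could reach it. Once the first injection is given, a same-day record of the untouched calf cannot be recovered.

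**Working it through.** The plan gives no figure on this point, and Section 6 rules out hypothesis testing, so there is nothing to reproduce. The check has two parts.

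**1. What is recorded when** (3.4.5 to 3.4.9 and Appendix 1)

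| Occasion | Table 3 assessment | VAS (one score, leg below knee) | BPI-DPN (pain diagram) |
|---|---|---|---|
| Day 0 pre-dose | no | yes | yes |
| Day 0 post-dose | yes | no | no |
| Day 14 pre-dose | yes | yes | no |
| Day 14 post-dose | yes | no | no |
| Day 21 | yes | no | no |
| Day 30 | yes | yes | yes |
| Day 60 | yes | yes | yes |

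- Four of the six Table 3 occasions, the ones closest to the injections, have no pain diagram alongside.
- The VAS is present at three of the six, but one score for the leg below the knee cannot separate foot pain from calf pain.
- None of these instruments records itching or erythema at the calf, the other two Grade 1 signs.
- The Day 14 pre-dose assessment follows the Day 0 injections, so it cannot serve as an untreated baseline.
- No section says that a Table 3 grade is to be read against any of these records.

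**2. How much a misgraded patient matters**

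Let q be the chance that one patient is misgraded at Grade 1. The documents give no rate, so q = 5%, 10% and 25% are assumptions. Taking patients as independent:

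P(at least one of n) = 1 − (1 − q)^n; expected number = n × q

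| q (assumed) | n = 4 | n = 12 | Expected in 12 |
|---|---|---|---|
| 5% | 1 − 0.95^4 = 18.5% | 1 − 0.95^12 = 46.0% | 0.6 |
| 10% | 1 − 0.90^4 = 34.4% | 1 − 0.90^12 = 71.8% | 1.2 |
| 25% | 1 − 0.75^4 = 68.4% | 1 − 0.75^12 = 96.8% | 3.0 |

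One misgraded patient shifts a cohort rate by 1/4 = 25 percentage points, and the rate over 12 patients by 1/12 = 8.3 points.

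**Which grades are exposed.** Grade 2 needs inflammation or phlebitis in addition to pain or swelling. The injection-site DLT in Section 3.2 needs active tissue necrosis of grade 3 or more. Existing pain alone meets neither.

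**The case against.** The strongest reply is that the plan already excludes unchanged neuropathic pain. The first column of Table 3 is headed as an adverse event, and Section 5.1, immediately after it, requires a new event or a deterioration. Findings before dosing belong to medical history, and underlying disease is an attribution option. The assessment concerns injection sites, each marked with indelible ink (Appendix 4), and no site exists before the first needle. On that view the Day 14 pre-dose tick simply follows up the Day 0 sites and does not show that a baseline was meant on Day 0. The BPI-DPN diagram shows before dosing whether pain reaches the calf.

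Much of this stands. A reader might infer that there is no same-day baseline at all. For pain location that is wrong, because the diagram provides one. A reader might also infer that every patient is exposed. The entry pain may be in the foot only, and diffuse leg pain is not automatically a reaction at a marked puncture.

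What does not stand is that the gap is thereby closed. The adverse event rules presuppose knowledge of what was present before dosing. For itching, erythema and skin condition of the calf, no Day 0 step supplies it. The diagram is not repeated at Day 0 post-dose, Day 14 or Day 21, and no text instructs the assessor or the analyst to use it when assigning or tabulating a Table 3 grade.

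**Conclusion.** The gap is real but limited. The first Table 3 assessment falls after the Day 0 injections in all three places that set the schedule, and the grades are linked to no pre-dose record. Grade 1 counts may include existing symptoms or omit true mild reactions. The direction and frequency are unknown. Under an assumed misgrading rate of 5% to 25%, the chance of at least one misgraded patient in a cohort of 4 is about 19% to 68%, at 25 points each.

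Two stronger readings are not supported. The first is that existing pain could drive the DLT, MTD or stopping rules: the injection-site DLT requires necrosis, and pain cannot trigger it. The second is that most cohorts would show false reactions. If calf involvement were 25% to 75%, the same formula would give 68% to over 99% per cohort, but only if every patient with calf pain were misgraded. The documents support neither that prevalence nor that certainty.

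The change is still worth making, because the affected table belongs to the primary endpoint and the missing record cannot be made later.

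**What to change.** 1. Add to the Day 0 pre-injection list (3.4.5.1), Section 4.2.11 and the Day 0 pre-dose column of Appendix 1 a record of pain, itching, erythema and skin findings on the calf to be injected, on the same form as the later assessments.
2. Report all raw Table 3 grades as now. Next to them, report reactions that are new or worse than the pre-dose record at the marked sites.
3. Count worsening within a grade as worse. A rule that counted only new signs or a higher grade would fail here: pain cannot rise from Grade 1 to Grade 2 without inflammation or phlebitis, so a patient with calf pain at baseline could have markedly worse pain after the injections and never be counted. In a safety study that would replace possible over-counting with systematic under-counting.

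Cost: a few minutes per patient at an existing visit, and one extra table column. Within-grade worsening calls for some judgement by the assessor; keeping the raw grades beside the adjusted count lets the reader see its effect.
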